6.5. Methods for Handling Missing Data

6.5.1. Adverse Event and Concomitant Medication Start Dates

If the end date is non-missing and the imputed start date is after the end date, the end date will be used as the start date.

(1) Missing day only

- If the month and year are the same as the month and year of the date of the start of study treatment, the date of the start of study treatment will be used.
- If the month and year are before the month and year of the date of the start of study treatment, the last day of the month will be used.
- If the month and year are after the month and year of the date of the start of study treatment, the first day of the month will be used.

(2) Missing day and month

- If the year is the same as the year of the date of the start of study treatment, the date of the start of study treatment will be used.
- If the year is before the year of the date of the start of study treatment, 31 December will be used.
- If the year is after the year of the date of the start of study treatment, 01 January will be used.
- (3) Missing day, month, and year
 - The date of the start of study treatment will be used.

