2.1.2.3. Clinical Experience

2.1.2.3.1. Pyruvate Kinase Deficiency

Mitapivat has been evaluated in 4 studies in adult subjects with pyruvate kinase deficiency, another hemolytic anemia. A Phase 2, open-label, safety and efficacy study (AG348-C-003 [DrivePK]) is ongoing. A Phase 3, double-blind, randomized, placebo-controlled study evaluating efficacy and safety in subjects who are not regularly transfused (AG348-C-006 [ACTIVATE]) has completed. Additionally, 2 open-label studies are ongoing: a Phase 3 study evaluating efficacy and safety in subjects who are regularly transfused (AG348-C-007 [ACTIVATE]) and a Phase 3 extension study for subjects who were previously enrolled in mitapivat studies (AG348-C-011).

In Study AG348-C-003, data from the initial 24 weeks of treatment (Core Period) indicated that approximately 50% of subjects (N=26) who received mitapivat (doses ranged from 50 to 300 mg BID) achieved maximum increases in Hb concentration that were >1 g/dL. Most increases were rapid. The median time to the first observation of an Hb concentration increase >1 g/dL above baseline was 10 days (range: 7 to 187 days). The Hb response was sustained in all 19 subjects who continued to receive mitapivat in the Extension Period. The median duration of exposure was 29 months (range: 22 to 35 months). Common adverse events (AEs), including headache and insomnia, occurred at the time of drug initiation and were transient; approximately 92% of the episodes of headache and 47% of the episodes of insomnia resolved within 7 days. The most common serious adverse events (SAEs), hemolytic anemia and pharyngitis, each occurred in 2 patients (4%) (Grace, Rose, et al, 2019). Additionally, AEs during the Extension Period were similar to those reported during the initial 24-week Core Period, indicating that safety was consistent with extended mitapivat administration (Grace, Layton, et al, 2019).

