6.3. Definitions

6.3.1. Study Drug and Study Treatment

In the Double-blind Period, both study drug and study treatment are defined as mitapivat or matched placebo.

In the OLE Period, both study drug and study treatment are defined as mitapivat.

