6.3.2. Start and End Dates of Study Treatment

The start of study treatment is the earliest date/time of administration of a non-zero dose of the study drug.

The end of study treatment is the latest date/time of administration of a non-zero dose of the study drug on or before the EODB period date/ EOS date.

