6.3.5. On-Treatment Period

The on-treatment period starts on the date of the start of study treatment and ends 28 days after the end of study treatment (including dose taper period).

Within the on-treatment period, there are two distinct treatment periods:

- Double-blind on-treatment period starts on the date of the start of study treatment and ends
 - 28 days after the end of study treatment, for subjects who discontinue study treatment during the Double-blind Period of the study
 - Before the start of the OLE treatment period, for subjects who continue onto the OLE Period of the study

• OLE on-treatment period applies only to subjects who complete the Doubleblind Period of the study, and starts with the first dose of open-label mitapivat in the OLE Period and ends 28 days after the end of study treatment.

For subjects who receive mitapivat in the OLE Period, assessments or events occurring on the date of first dose of mitapivat in the OLE Period will be included in the analysis of the data from the double-blind on-treatment period, except for AEs and concomitant medications reported for subjects in the placebo arm which will be included only in the analysis of the data from the OLE on-treatment period.

Data listings will include all assessments and events, with those that occur outside of the on-treatment period flagged.

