6.5.3. Exposure

No imputation will be done for the date of the first dose of study drug.

If the date of the last dose of study drug is missing or partially missing, it will be imputed as follows (separately for each period):

• If the last date of study drug is completely missing and there is no End of Treatment Disposition electronic case report form (eCRF) page for the study drug AND there is no death date, the subject should be considered to be ongoing and the EODB period date/EOS date, will be used as the last dosing date. • If the last date of study drug is completely or partially missing and there is EITHER an End of Treatment Disposition eCRF page for the study drug OR a death date (on or before the EODB period date/EOS date), then the imputed last dose date is:

=Last day of the year, if only the year is available and Year <Year of min(end of treatment [EOT] date, death date)

=Last day of the month, if both the year and month are available and Year=Year of min(EOT date, death date) and Month <Month of min(EOT date, death date)

=min(EOT date, death date), for all other cases

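### Partial AE onset dates are imputed against the first double-blind dose only, so some AEs that begin after a placebo subject starts open-label mitapivat are dated into the placebo period

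*SAP*

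**What the plan says.** SAP 6.3.2 has one anchor date: "The start of study treatment is the earliest date/time of administration of a non-zero dose of the study drug". SAP 6.3.1 says that in the Double-blind Period "both study drug and study treatment are defined as mitapivat or matched placebo". For a placebo subject the anchor is therefore the first placebo dose.

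SAP 6.5.1 compares every partial AE start date with that anchor:
- Day missing, later month: the known parts of the date "are after the month and year of the date of the start of study treatment, the first day of the month will be used".
- Day and month missing: "If the year is after the year of the date of the start of study treatment, 01 January will be used". If the year is the same as that of the anchor, "the date of the start of study treatment will be used".
- Wholly missing: the anchor date is used.

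If the imputed start falls after a known end date, the end date becomes the start. That check can only move a start date earlier.

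SAP 6.3.5 then divides AEs by date. The "Double-blind on-treatment period starts on the date of the start of study treatment and ends", for subjects who continue, before the open-label treatment period begins with the first open-label dose. SAP 7.7 tabulates the two periods separately. Under 6.3.5, a placebo subject's AE dated on the day of the first open-label dose counts in the extension only.

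**The concern.** For a placebo subject the switch at Week 48 is a first exposure to mitapivat. At the first double-blind dose the imputation is conservative: an AE known only to the month of that dose is set to the dose date and becomes treatment-emergent. At the switch the same section does the reverse and dates the AE to before mitapivat was taken.

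Elsewhere the SAP keeps the periods apart. Section 6.3.4.2 re-anchors the extension baseline of placebo subjects to the start of open-label mitapivat, 6.4.5 defines separate extension visit windows, and 6.5.3 says of a missing last-dose date that "it will be imputed as follows (separately for each period". Section 6.5.1 has no such provision.

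What is at stake is the allocation of AEs that arise when mitapivat is started. Protocol 2.1.2.3.1 says of an earlier study in pyruvate kinase deficiency: "Common adverse events (AEs), including headache and insomnia, occurred at the time of drug initiation and were transient". In former placebo subjects such AEs would fall just after the switch, where the rule misplaces them. The extension tables would lose AEs that began on mitapivat, and the placebo column could gain them.

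**Working it through.** The documents give no figure on this point, so the rules were applied to calendar dates.

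**Example (dates assumed).** First placebo dose 10 March 2022; Day 337 is 336 days later, 9 February 2023. Protocol Table 1 puts the first open-label dose on the evening of the Week 48 visit (Day 337, window ±12 days).

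| True onset | Day missing | Only year known | Wholly missing |
|---|---|---|---|
| 19 Feb 2023 | 1 Feb 2023, placebo | 1 Jan 2023, placebo | 10 Mar 2022, placebo |
| 21 Mar 2023 | 1 Mar 2023, extension | 1 Jan 2023, placebo | 10 Mar 2022, placebo |
| 15 Mar 2024 | 1 Mar 2024, extension | 1 Jan 2024, extension | 10 Mar 2022, placebo |

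The missing-day error is confined to the switch month and vanishes if the switch was on the 1st. The year-only error is confined to the switch year and vanishes if the switch was on 1 January. With starts spread evenly, about 336/365 = 92% of subjects switch in a later calendar year than they started, so 01 January applies. For the rest the first placebo dose applies. Both dates lie in the placebo period.

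**Share misplaced.** Assume that switch dates are spread evenly over the year and that true onset is uniform over the H days beginning with the switch date.

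*Day missing.* For a switch on day d of a month with L days, min(H, L − d + 1) of the H onset days are misplaced when d ≥ 2, and none when d = 1. With H = 28, summing over d:
- 31-day month: 3 × 28 + (27 + … + 1) = 84 + 378 = 462
- 30-day month: 2 × 28 + 378 = 434
- 28-day February: 378
- Year: 7 × 462 + 4 × 434 + 378 = 5,348 of 365 × 28 = 10,220, or 52%

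*Only year known.* For a switch on day y of the year, min(H, 365 − y + 1) onset days are misplaced when y ≥ 2. With H = 28: 337 × 28 + 378 = 9,814 of 10,220, or 96%.

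An enumeration of all first-dose dates over four assumed years (2021–2024), with the switch at Day 337 and at offsets of ±6 and ±12 days, agrees:

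| Onset within | Day missing | Only year known | Wholly missing |
|---|---|---|---|
| 28 days | 52% | 96% | 100% |
| 84 days | 18% | 88% | 100% |
| 364 days | 4% | 50% | 100% |

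**With a second anchor at the first open-label dose**, the first two columns fall to 0%; wholly missing dates stay at 100% unless given their own rule. The price is the reverse error: of AEs that truly began in the 28 days before the switch, 52% (day missing) or 96% (only year known) would move to the extension, against 0% now.

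**Effect on the arm contrast.** Let b_P and b_M be the proportions of placebo-arm and mitapivat-arm subjects who gain a back-dated AE in the double-blind table. The difference in AE incidence, mitapivat minus placebo, shifts by b_M − b_P. It favours mitapivat only if b_P > b_M.

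**The case against.** **Direction.** A reader might infer that the bias runs one way and makes mitapivat look safer. The documents do not establish that. SAP 6.5.1 applies to both arms, and mitapivat-arm subjects cross the same boundary, so their partly dated extension AEs also move back into the double-blind table. With 160 and 80 planned subjects, about twice as many mitapivat-arm subjects are open to it. Whether b_P exceeds b_M depends on initiation AEs clustering in former placebo subjects. That is plausible, but it is an assumption. Protocol 4.3 itself reports similar insomnia frequencies on mitapivat and placebo in pyruvate kinase deficiency (17.5% and 17.9%, maximum 50 mg twice daily).

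**Size.** A reader might note that, in a 30-day month, the rule sends about 29 of every 30 missing-day AEs in the switch month to the placebo period. That is not an error rate, because it includes AEs that truly began on placebo and are placed correctly. The rate among AEs beginning within 28 days after the switch is about 52%.

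**Primary report.** A reader might infer that these AEs will certainly appear as placebo events in the primary report. SAP 6.4.1 keeps data after the end of the Double-blind Period out of that report, including from imputations. An AE first recorded at Week 52 might be excluded on that ground. But 6.4.1 does not say how an AE is assigned when its partial date spans the switch, so it leaves the matter open.

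**Frequency.** Protocol 9.2.1 requires an onset date for each AE and collects AEs at every visit; the switch takes place at a visit and the next is at Week 52. Year-only and undated AEs should be rare. This stands.

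**Switch-day rule.** The 6.3.5 provision settles AEs dated on the switch day. It is not a general rule for doubtful dates, and it cannot act once the imputed date precedes the switch.

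**Conclusion.** The gap in SAP 6.5.1 is real, and no other section closes it. For placebo-arm subjects it misplaces post-switch AEs in three defined cases: day missing in the switch month, only the switch year known, and wholly undated. Among AEs beginning within 28 days after the switch, about 52% of missing-day and 96% of year-only AEs are dated back, assuming evenly spread switch dates and uniform onset.

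The absolute number cannot be derived, because the documents give no rate of partial onset dates; it is probably small. The effect on the arm comparison is not strictly one-way, and a more favourable picture for mitapivat rests on the clustering assumption above. Efficacy is unaffected. This is a modest correction to the safety analysis, worth making before unblinding.

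**What to change.** In SAP 6.5.1, add the first open-label dose as a second anchor for placebo-arm subjects:
- If the known part of the AE start date equals the month and year of that dose (day missing), or its year (day and month missing), impute the date of that dose. If the AE end date is earlier than the dose, keep the existing rule.
- Keep the existing rule for later months and years, so that those AEs are not pulled back to the switch.
- State an explicit rule for wholly missing dates.

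List all AEs in both arms whose partial date spans the switch, and show the double-blind AE summary under both assignments. Say in 6.4.1 how such AEs are treated in the primary report. As 6.5.1 also governs concomitant medication start dates, say whether the second anchor applies to them.

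The cost is a few SAP sentences, a small programming change, one listing and one repeated table. The downside is the reverse error: some AEs that truly began on placebo shortly before the switch move to the extension. That is conservative for mitapivat and consistent with the switch-day rule in SAP 6.3.5, and the SAP should acknowledge it.

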6.5.2. Adverse Event and Concomitant Medication End Dates

If the start date is non-missing and the imputed end date is before the start date, the start date will be used as the end date. If the death date is available and the imputed end date is after the death date, the death date will be used as the end date. If an imputation for an AE end date results in an AE end date that is after the EODB period date/EOS date, the AE will be considered as ongoing at the EODB period date/EOS date.

- (1) Missing day only
 - The last day of the month will be used.
- (2) Missing day and month
 - 31 December will be used.
- (3) Missing day, month, and year
 - The event will be regarded as ongoing.

6.5.3. Exposure

No imputation will be done for the date of the first dose of study drug.

If the date of the last dose of study drug is missing or partially missing, it will be imputed as follows (separately for each period):

• If the last date of study drug is completely missing and there is no End of Treatment Disposition electronic case report form (eCRF) page for the study drug AND there is no death date, the subject should be considered to be ongoing and the EODB period date/EOS date, will be used as the last dosing date. • If the last date of study drug is completely or partially missing and there is EITHER an End of Treatment Disposition eCRF page for the study drug OR a death date (on or before the EODB period date/EOS date), then the imputed last dose date is:

=Last day of the year, if only the year is available and Year <Year of min(end of treatment [EOT] date, death date)

=Last day of the month, if both the year and month are available and Year=Year of min(EOT date, death date) and Month <Month of min(EOT date, death date)

=min(EOT date, death date), for all other cases

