7.4.1. Treatment Duration and Exposure

Duration of exposure to study drug will be summarized as a continuous variable as well as in categories.

• Duration of exposure (days)=(last dose date-first dose date+1)

Duration of exposure (weeks)=(last dose date-first dose date+1)/7

- Duration of exposure (years)=(last dose date-first dose date+1)/365.25
- Double-blind Period: the categories will be >0-6, >6-12, >12-24, >24-36, >36-48, and >48 weeks
- OLE Period: the categories will be >0-0.5, >0.5-1, >1-2, >2-3, >3-4, >4-≤5, and >5 years.

Compliance will be summarized based on percentage of tablets taken, where

• Percentage of tablets taken =100×(total number of tablets administered)/(total number of tablets intended)

Total number of tablets administered = total number of tablets dispensed – tablets returned

Duration of prescription = end date of prescription-start date of prescription +1

Total number of tablets intended = sum of number of tablets intended over all prescription periods.

Number of tablets intended during each prescription period = prescribed dosing frequency \times number of tablets intended for each administration \times duration of the prescription. Prescribed dosing frequency takes value of 1 and 2 for QD and BID, respectively

Percentage of tablets taken will be summarized by treatment arm. The frequency of subjects whose compliance is <80%, 80-100%, >100-120%, and >120% will be summarized.

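### The SAP's last-dose imputation overrides a known month when that month lies in an earlier calendar year than end of treatment or death

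*SAP*

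**What the plan says.** SAP 6.5.3 (Exposure) covers a missing last-dose date, separately for each period. The relevant rule begins "If the last date of study drug is completely or partially missing and there is EITHER an End of Treatment Disposition eCRF page" and applies equally where there is a death date. Call the earlier of the EOT and death dates the reference date. The three clauses are:

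1. Year only known: "Last day of the year, if only the year is available and Year <Year of min(end of treatment [EOT] date, death date").
2. Year and month known: "Last day of the month, if both the year and month are available and Year=Year of min(EOT date, death date"), with the further condition "and Month <Month of min(EOT date, death date").
3. Residual: "min(EOT date, death date), for all other cases".

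The last-dose date is then used in two places:

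- SAP 7.4.1: "Duration of exposure (days)=(last dose date-first dose date+1").
- SAP 6.3.2 and 6.3.5: "The end of study treatment is the latest date/time of administration of a non-zero dose of the study drug", and "The on-treatment period starts on the date of the start of study treatment and ends 28 days after the end of study treatment".

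**The concern.** Clause 2 tests for an equal year and clause 1 is confined to records with the year alone. No clause handles a known month in an earlier year, so such a record drops to clause 3 and receives a date in a later calendar year than the one the site recorded.

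This does not look intended. Clauses 1 and 2 both refuse to carry dosing beyond the recorded year or month, and the same gap inside one calendar year is handled properly. SAP 6.5.1, on start dates of adverse events and medications, compares month and year together, so the SAP already contains the construction that is missing here.

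At stake are exposure duration and, where the on-treatment window depends on the last dose, the line between on-treatment and post-treatment events. A 48-week double-blind period and a five-year extension make year-end crossings possible in either period.

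**Working it through.** The documents state no figure that depends on this rule, so there is nothing to reproduce. The check applies the three clauses literally and compares them with a version in which clause 2 asks whether the recorded (year, month) is earlier than the (year, month) of the reference date. All calendar dates below are assumptions; none comes from the documents.

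**Date imputed by each rule**

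| Recorded last dose | Reference date | Clause met | SAP rule | Joint comparison | Excess |
|---|---|---|---|---|---|
| Sep 2022 | 15 Nov 2022 | 2 | 30 Sep 2022 | 30 Sep 2022 | 0 days |
| 2022 only | 15 Jan 2023 | 1 | 31 Dec 2022 | 31 Dec 2022 | 0 days |
| Dec 2022 | 1 Jan 2023 | 3 | 1 Jan 2023 | 31 Dec 2022 | 1 day |
| Dec 2022 | 15 Jan 2023 | 3 | 15 Jan 2023 | 31 Dec 2022 | 15 days |
| Nov 2022 | 15 Jan 2023 | 3 | 15 Jan 2023 | 30 Nov 2022 | 31 + 15 = 46 days |
| Oct 2022 | 15 Jan 2023 | 3 | 15 Jan 2023 | 31 Oct 2022 | 30 + 31 + 15 = 76 days |

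Rows 2 and 6 show the anomaly: with the same reference date, the year alone gives 31 December 2022, while the more informative October 2022 gives 15 January 2023.

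**Where the two rules differ.** Take every recorded month in 2022 to 2024 with a reference date 0 to 199 days after the first of that month: 36 × 200 = 7200 combinations. The rules disagree in 1671. All have a recorded year earlier than the reference year, and the SAP date is always the later one, by 1 to 170 days. This shows where the fault lies; it does not estimate how often it will occur.

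**Effect on exposure (October example, first dose assumed 1 June 2022)**

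- SAP rule: 1 June 2022 to 15 January 2023 inclusive = 229 days, or 229/7 = 32.7 weeks.
- Joint comparison: 1 June to 31 October 2022 inclusive = 153 days, or 153/7 = 21.9 weeks.
- Difference: 229 − 153 = 76 days. In the double-blind categories of SAP 7.4.1 the subject moves from >12-24 to >24-36 weeks.

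**Effect on the on-treatment window (same example)**

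- SAP rule: 15 January 2023 + 28 days = 12 February 2023.
- Joint comparison: 31 October 2022 + 28 days = 28 November 2022.

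The last day of the recorded month is the latest date the record allows, so if the recorded month is right, each excess is a minimum.

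**The case against.** The gap in the clauses stands: no other section caps the imputed date at the recorded month. The objections that carry weight concern consequence and size.

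**Post-treatment data.** A reader might infer that, in the October example, 76 further days of adverse events and laboratory values enter the on-treatment summaries. The documents do not support that. Protocol 9.2.1 ends routine AE recording 28 days after the last dose; after the Safety Follow-up visit only related SAEs are to be reported. The schedule of assessments places that visit 28 days (+4) after the last dose and shows no later laboratory visit for a subject who has stopped. For double-blind discontinuers, SAP 2 ends the period at safety follow-up, and SAP 6.4.1 keeps later data out of the primary report. For subjects who enter the OLE, SAP 6.3.5 closes the double-blind window at OLE start whatever date is imputed. If sites follow these rules, most of the extra window holds no routine data. What remains is a death, a late related SAE or a value from a late visit.

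**Subjects lost to follow-up.** A reader might also infer that these subjects are hit hardest because their EOT date trails the last dose. Neither document says how an EOT date is set for them; Protocol 7.3 gives no rule. If their last-dose date is wholly missing, both versions of the rule give the reference date.

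**Narrow trigger.** The fault needs a missing day, a known month and year, and a reference date in a later calendar year. Double-blind dosing is kept in a diary and tablets are returned at visits, so few records should qualify. The documents give no count.

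**Conservatism.** One could defend a later date as cautious for safety. Clauses 1 and 2 do not follow that principle, so it does not explain clause 3.

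**Conclusion.** The rule is wrong as written for one class of record, and the matter is minor. When month and year are known and the year is earlier than that of the reference date, the imputed last dose contradicts the record and exposure is overstated. For double-blind discontinuers and in the OLE, the on-treatment window also starts its 28 days too late. For subjects who continue into the OLE, only the double-blind last dose and exposure duration are affected.

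The size per subject runs from 1 day upward and depends on the gap between last dose and the EOT or death date, which the documents do not give. The effect on the window assumes that the imputed date serves as the end of study treatment, which SAP 6.3.2 implies but does not state.

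It would be a mistake to read this as a threat to the efficacy conclusions. The primary and key secondary endpoints count transfused units over study-day windows in the FAS (SAP 7.6.1, 7.6.2), with non-response determined by study withdrawal. Compliance uses tablet counts and prescription dates (SAP 7.4.1). Neither uses the last-dose date.

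**What to change.** Reword the condition of the second clause in SAP 6.5.3 so that it applies when year and month are both known and either (a) the recorded year is earlier than the year of min(EOT date, death date), or (b) the years are equal and the recorded month is earlier. In both cases impute the last day of the recorded month. The other two clauses stay as they are and same-year results do not change.

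The cost is one clause in the SAP and the matching line of the derivation program. No data collection, sample size or protocol text is affected.
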